9.3.3. Exclusion Criteria for the PM/CRT-P Cohort

No additional Exclusion Criteria for the PM/CRT-P Cohort.

9.3.4. Exclusion Criteria for the Non-device Cohort (ESC Guideline 2016 Indicated but not implanted)

Subjects who meet any one of the following criteria (Table 9.3-3) will be excluded from the Non-device cohort (ESC Guideline 2016 indicated but not implanted) of the study.

Table 9.3-3: Exclusion Criteria for the Non-device Cohort (ESC Guideline 2016 Indicated but not implanted)

1. Subjects who have recovered from a ventricular arrhythmia causing hemodynamic instability
2. Subject with any ICD or CRT-D, PM or CRT-P device implanted at any time prior to enrollment.

Abbreviations: CRT-D = cardiac resynchronization therapy-defibrillator; CRT-P = cardiac resynchronization therapy-pacemaker; ICD = implantable cardioverter-defibrillator; PM = pacemaker

10. Subject Accountability

10.1. Point of Enrolment

Subjects will only be enrolled in this registry study if they meet all eligibility criteria and provide written informed consent. If a subject is found not to meet all applicable eligibility criteria, the subject will be withdrawn from the study; any points of ineligibility must be clearly documented in the enrolment/screening log. These subjects will be considered

consent ineligible as discussed in Section 10.3, and will not count towards the enrolment ceiling. Any subject that signs consent and meets all inclusion criteria and does not meet any Exclusion Criteria will be enrolled in the study. Any reportable events, as defined in Section 20 of this CIP, must be collected after written informed consent is obtained.

Subjects enrolled under protocol version C deviating from eligibility criteria of protocol version D will be withdrawn from the study. Other subjects previously not meeting eligibility criteria of protocol version C, but now meeting eligibility criteria of protocol version D, will be accepted under protocol version D and no protocol deviation will need to be documented in the eCRF.

10.2. *Withdrawal*

All subjects enrolled in this registry study (including those withdrawn from the clinical study or lost to follow-up) shall be accounted for and documented. If a subject withdraws from the study, the reason(s) shall be reported. If such withdrawal is due to problems related to investigational device safety or performance, the investigator shall ask for the subject's permission to follow his/her status/condition outside of the clinical study.

All applicable eCRFs should be completed up to the point of subject withdrawal. Subjects who are "lost-to-follow-up" should have 3 documented failed phone call attempts to contact the subject as well as a certified letter sent to the subject without a response prior to study withdrawal or termination. A death note will need to be provided together with the serious adverse event (SAE) event description on the Adverse Event (AE) form. Additional data may no longer be collected after the point at which a subject has been withdrawn from the study or withdraws his/her consent, for whatever reason. All open AEs should be closed or documented as chronic or continuing at the end of the study. Data collected up to the point of subject withdrawal may be used. A Study Withdrawal eCRF page should be completed at this time. A retrospective cancelling of subject data collection should be expressed explicitly by the subject so that all data can be removed from the database.

10.3. *Subject Status and Classification*

Consent ineligible subject

A study subject who has signed informed consent but is found to not meet eligibility criteria will be considered a consent ineligible subject and will not count towards the enrolment ceiling. There are no follow-up or AE reporting requirements for consent ineligible subjects. The original signed informed consent must be maintained in the center's administrative file as original or e-copy as part of the hospital patient chart.

Active enrolled subject

A study subject who meets the eligibility criteria as per Section 9.2 and Section 9.3 and has signed and dated the subject informed consent form (ICF) is considered actively enrolled in the study. These subjects are followed in accordance with the CIP follow-up schedule and included in the foreseen study analysis. The original signed subject ICF and any applicable documentation must be maintained in the center's subject paper or electronic file. All applicable electronic Case Report Form (eCRFs) per the CIP must be completed.

10.4. *Enrolment Controls*

Centers are allowed to enroll up to 20% of subjects in each of the 4 defined Subject Cohorts. This translates into the following allowed maximum subject numbers per center:

- ICD:23 to 54 subjects*
- CRT-D: 19 to 50 subjects*
- PM/CRT-P:34 to 40 subjects
- Non-device:34 to 60 subjects
(ESC Guideline 2016 Indicated but not implanted)

* Variable; depending on the total number of enrolled subjects in this study cohort.

If a center wishes to exceed these limits, the center must obtain prior approval from the sponsor or sponsor's delegated representative.

As soon as a minimum of 556 eligible subjects are entered into the study database, the closure of enrolment can begin. All sites will be informed that enrolment has closed. After closure of enrolment has been communicated, sites must obtain approval from the sponsor or the sponsor's delegated representative for all remaining subjects who are consented but who are not yet enrolled into the study database.

A maximum of 950 subjects will be allowed to be followed and entered into the study database.

11. Study Methods

11.1. *Data Collection*

Details for data collection are shown in Table 11.1-1. Data collection will take place at the following time points:

- Enrolment and Consenting Clinic Visit (Day 0, 0 to 45 days post implant procedure, alternative minimum > 3months post MI, PCI, or CABG required). The date of signature on the informed consent form is the time point of enrolment.
- Six-monthly Visit (180 ± 60 days post enrolment and multiplies until Close-out Visit) (required)
- Re-implant or new device implant post enrolment (optional)
- Interim Visit and Event Report (SAE/SADE related clinical care visit) (Following study site specific SOC, optional)
- Close-out Clinic Visit (see table 8.1-1) (required)

All clinic visits that occur outside the specified protocol visit window will be classified as "Unscheduled CIP Visits". Unscheduled visits triggered by a specific event (e.g. adverse event, Latitude alert, patient request etc.) and not by standard routine control (e.g. device check-up standard by the institution, wound check, standard echo or ECG, blood analysis etc.) must be documented.

CIP defined visits that occur outside the specified visit window will be documented as a CIP deviation.

All data collected according to the Data Collection Requirements (Table 11.1-1) and specified in Sections 11.2 to 11.9 are to be appropriately noted in the eCRF.

Table 11.1-1: Data Collection Requirements

Procedure/Assessment	Enrolment and Consenting Clinic Visit	Follow-Up Visits			
	Day 0 (required) (0 to 45 days post implant procedure, or minimum ≥ 3 months post MI, PCI, or CABG)	6-monthly Visit (required) (180 ± 60 days post enrolment and multiplies until Close-out Visit)	Re-implant or New Device Implant post Enrolment (optional)	Interim/Unscheduled Visit and Event Report (optional) (SAE/SADE related clinical care visit)	Close-out Clinic Visit (required) (see figure 8.1-1)
Informed consent form, including informed consent signature and date	X	--	--	--	--
Inclusion criteria / exclusion criteria	X	--	--	--	--
Demographic data	X	--	--	--	--
Clinical assessment	X	--	X	--	X
Medical history/co-morbidities	X	--	X	--	--
LVEF, intrinsic or paced	X	SOC	SOC	--	SOC
QRS, intrinsic	X	--	--	--	--
QRS, intrinsic or paced	--	--	--	--	X
Current concomitant medications	X	--	X	--	X
Documentation of implanted devices	X	--	X	--	--
ECG recording pre-implant upload	SOC	--	SOC	--	--
ECG recording post implant (paced) upload	SOC		SOC	--	SOC
Echocardiography data collection	SOC	SOC	SOC	--	SOC
Device assessment/Interrogation (for devices)	SOC	SOC	SOC	--	SOC
Standard Biomarkers for heart failure+ other	SOC	--	--	--	SOC
Adverse events assessment review	--	X	X	X	X
Adverse events reporting (SAE, SADE, ADE, DD information)	X	X	X	X	X
Latitude device data collection (for subjects implanted with a device)	X	X	X	X	X

	Enrolment and Consenting Clinic Visit Day 0 (required) (0 to 45 days post implant procedure, or minimum ≥ 3 months post MI, PCI, or CABG)	Follow-Up Visits			
		6-monthly Visit (required) (180 ± 60 days post enrolment and multiplies until Close-out Visit)	Re-implant or New Device Implant post Enrolment (optional)	Interim/Unscheduled Visit and Event Report (optional) (SAE/SADE related clinical care visit)	Close-out Clinic Visit (required) (see figure 8.1-1)
Procedure/Assessment					
MRI scan information	SOC	SOC	SOC	SOC	SOC
Physician's judgment on therapy status / outcome / CRT therapy delivery / defibrillator therapy	X	X	X	--	X
Risk factor assessment	X	X	X	X	X
Protocol deviations	X	X	X	X	X

SOC = according to standard of care; X = required; -- = not required

Abbreviations: ADE = adverse device effect; CRT = cardiac resynchronization therapy; DD = device deficiency; ECG = electrocardiogram; LAT = Latitude reporting system; LSLV = last subject last visit; LVEF = Left ventricular ejection fraction; MI = myocardial infarction; MRI = magnetic resonance imaging; NYHA = New York Heart Association; SADE = serious adverse device effect; SAE = serious adverse events; SOC = required if center's standard of care; X = required; -- = not required.

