	
All device systems are on the market in Japan, and will be implanted per standard of care (SOC) and BSC Instructions for Use (IFU) for the respective devices should be followed.
 
Neither the devices nor the implant procedure are part of this study. The decision as to which device any subject receives is to be determined by the investigator and is not part of this study.
 
Device system use and programming will need to follow SOC, devices IFUs and must follow CIP programming requirements. All devices in the study must be intended to be connected to the Latitude system.

Study Design	
This is a prospective, non-randomized, multicenter, multi-cohort clinical outcome registry study to evaluate SOC.

Planned Number of Subjects	
It is planned to enroll a minimum of 556 to power all primary endpoint for each cohort.
 
As soon as a minimum of 556 eligible subjects are entered into the study database, the closure of enrolment can begin. The maximum number of followed study subjects is 950.
 
The event dependent character of the study, and the calculated necessary minimum sample size may allow early enrollment closure of the study enrollment.

Planned Number of Investigational Sites / Countries	
Approximately 40 investigational sites in Japan will be included. If a site does not enroll a subject within a 3-month time period, the site may be closed for enrolment and replaced at the discretion of the sponsor.

Primary Safety Endpoint(s)	
Not applicable

Heart Failure Indication and Sudden Cardiac Death Prevention Trial Japan
HINODE

Primary Effectiveness Endpoints	
Defibrillator Cohort (including ICD and CRT-D Cohorts): Composite rate of first appropriately treated ventricular arrhythmia (by anti-tachycardia pacing [ATP] or shock) or life-threatening symptoms associated to ventricular arrhythmia (defined as hemodynamic instability which requires treatment), whichever comes first under MADIT Arm B or C programming conditions in a study population with a majority of Japanese subjects
 
PM/CRT-P Cohort: All-cause mortality in subjects with a maximum of 3 risk factors (analyzed for MADIT II data)
 
Non-device Cohort (ESC Guideline 2016 Indicated but not implanted): All-cause mortality in the subject cohort with 2 to 5 predefined SCD driving risk factors

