Statistical Test Method (continued)	
 • The primary endpoints above will be performed for ICD and CRT-D cohorts combined (primary analysis) as well as for ICD and CRT-D treated subjects separately (for descriptive purpose). • For PM/CRT-P treated subjects, the all-cause mortality free-rate (survival rate) from implant will be calculated as the proportion of actively enrolled subjects who are alive 12 months after implant. The null hypothesis will be rejected and the endpoint considered met if the lower one-sided 97.5% confidence bound for the proportion of subjects with no death is greater than 80.0%. • For Non-device subjects (ESC Guideline 2016 Indicated but not implanted), the all-cause mortality free-rate (survival rate) from enrolment will be calculated as the proportion of actively enrolled subjects who are alive 12 months after enrolment. The null hypothesis will be rejected and the endpoint considered met if the lower one-sided 97.5% confidence bound for the proportion of subjects with no death is greater than 80.0%. • Exploratory analyses for ICD and CRT-D Cohorts combined versus Non-Device Cohort (ESC Guideline 2016 Indicated but not implanted): propensity score matching comparison of all-cause mortality rate and composite rate of HF events between pooled cohorts with device (ICD and CRT-D) versus the Non-Device Cohort regarding 7 risk factors at baseline (NYHA Class III or IV, renal dysfunction [chronically BUN >26 mg/dL / ≥ 9.28 mmol/L], diabetes type I and II, chronic atrial fibrillation [permanent or persisting according to ESC Guideline 2016], prior MI, age >70 years, smoking today or during last 5 years). 
Further details on analytical methods can be found in Section 12 of the CIP

Sample Size Parameters	
ICD Treated Subjects:
 
The minimum required sample size to statistically power the ventricular arrhythmia associated symptoms free-rate through 12 months post implant is 117 subjects. Sample size was calculated assuming a 95.0% ventricular arrhythmia associated symptoms free-rate, a performance goal of 85.0%, one-sided alpha level of 0.025, 90% power, and 20% attrition.

Heart Failure Indication and Sudden Cardiac Death Prevention Trial Japan
Hinode

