Sample Size Parameters (continued)	
Although the final sample size of 117-270 for ICD treated subjects is higher than that required to power the primary endpoint, a sample size of up to 270 ensures that there will be a sufficient number of subjects to evaluate the primary endpoint, as well as provide ample data to characterize the safety, performance and efficacy profiles based on secondary and additional endpoints.
 
CRT-D Treated Subjects:
 
The minimum required sample size to statistically power the ventricular arrhythmia associated symptoms free-rate through 12 months post implant is 95 subjects. Sample size was calculated assuming a 97.0% ventricular arrhythmia associated symptoms free-rate, a performance goal of 87.0%, one-sided alpha level of 0.025, 90% power, and 20% attrition.
 
Although the final adjustable sample size of 95-250 for CRT-D treated subjects is higher than that required to power the primary endpoint of the study arm, a sample size of up to 250 ensures that there will be a sufficient number of subjects to evaluate the primary endpoint, as well as provide ample data in the study arm to characterize the safety, performance and efficacy profiles based on secondary and additional endpoints.
 
PM/CRT-P Treated Subjects:
 
The minimum required sample size to statistically power the all-cause mortality free-rate (survival rate) through 12 months post implant is 172 subjects. Sample size was calculated assuming a 90.0% all-cause mortality free-rate (survival rate), a performance goal of 80.0%, one-sided alpha level of 0.025, 90% power, and 20% attrition.
 
Although the final sample size of 200 for PM/CRT-P treated subjects is higher than that required to power the primary endpoint, a sample size of 200 ensures that there will be a sufficient number of subjects to evaluate the primary endpoint, as well as provide ample data to characterize the safety, performance and efficacy profiles based on secondary and additional endpoints.

---	---

Heart Failure Indication and Sudden Cardiac Death Prevention Trial Japan
Hinode

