Sample Size Parameters (continued)	
Non-device Subjects (ESC Guideline 2016 Indicated but not implanted):
 
The minimum required sample size to statistically power the all-cause mortality free-rate (survival rate) through 12 months after enrolment is 172 subjects. Sample size was calculated assuming a 90.0% all-cause mortality free-rate, a performance goal of 80.0%, one-sided alpha level of 0.025, 90% power, and 20% attrition.
 
The final sample size of 300 for Non-device subjects is higher than that required to power the primary endpoint in order to ensure that there will be a sufficient number of subjects to compare the rate of sudden cardiac death in the non-device cohort with the rate of appropriately treated ventricular arrhythmias or sudden cardiac death in the defibrillator cohort (ICD, CRT-D).
 
In case of low enrollment rates, enrollment may be closed after the statistically required calculated minimum sample size for each cohort.

---	--

3. Table of Contents

1. TITLE PAGE	1
2. SYNOPSIS	6
3. TABLE OF CONTENTS.....	20
3.1. Table of Figures.....	25
3.2. Table of Tables	25
4. INTRODUCTION	26
5. DEVICE DESCRIPTION.....	27
6. STUDY OBJECTIVES	28
7. STUDY ENDPOINTS	29
7.1. Primary Endpoints.....	29
7.2. Secondary Endpoints	29
7.3. Additional Endpoints.....	30
8. STUDY DESIGN	30
8.1. Scale and Duration.....	31
8.2. Treatment Assignment	33
8.3. Justification for the Study Design.....	33
9. SUBJECT SELECTION.....	33
9.1. Study Population and Eligibility.....	33
9.2. Inclusion Criteria	33
9.2.1. General Inclusion Criteria.....	34
9.2.2. Inclusion Criteria for the ICD Cohort.....	35
9.2.3. Inclusion Criteria for the CRT-D Cohort.....	36
9.2.4. Inclusion Criteria for the PM/CRT-P Cohort	37
9.2.5. Inclusion Criteria for the Non-device Cohort (ESC Guideline 2016 Indicated but not implanted)	38
9.3. Exclusion Criteria	39
9.3.1. General Exclusion Criteria	39
9.3.2. Exclusion Criteria for the ICD and CRT-D Cohorts	41
9.3.3. Exclusion Criteria for the PM/CRT-P Cohort	41

9.3.4. Exclusion Criteria for the Non-device Cohort (ESC Guideline 2016 Indicated but not implanted)	41
10. SUBJECT ACCOUNTABILITY.....	41
10.1. Point of Enrolment.....	41
10.2. Withdrawal.....	42
10.3. Subject Status and Classification.....	42
10.4. Enrolment Controls	43
11. STUDY METHODS	43
11.1. Data Collection	43
11.2. Study Candidate Screening	47
11.3. Informed Consent	47

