PM = pacemaker; CRT-P = cardiac resynchronization therapy-pacemaker.

Sample sizes for primary endpoints were calculated employing exact binomial methods in nQuery + nTerim 3.0.

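### The pooled enrolment-closure trigger of 556 does not secure each cohort's own minimum, although the plan says 556 powers every cohort

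*Combined protocol and SAP*

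**What the plan says.** The Synopsis (Planned Number of Subjects), Section 8.1 and Section 10.4 all give the same trigger: "As soon as a minimum of 556 eligible subjects are entered into the study database, the closure of enrolment can begin". None of them adds a condition on any cohort. Section 10.4 then has sites told that enrolment is closed, after which consented subjects not yet in the database need sponsor approval. Its other controls are per-centre maxima and an overall ceiling of 950.

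The Synopsis attaches a purpose to the figure: "It is planned to enroll a minimum of 556 to power all primary endpoint for each cohort". Section 12.2.2 says the same.

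Cohort floors appear elsewhere. The Synopsis, Section 8.2 and Section 12.1.6 give ranges of 117–270 (ICD), 95–250 (CRT-D), 172–200 (PM/CRT-P) and 172–300 (Non-device). Table 12.1-1 labels the lower ends as required minimum enrolment. The end of the Synopsis sample-size text says that, if enrolment is slow, "enrollment may be closed after the statistically required calculated minimum sample size for each cohort". Section 12.1.6 repeats that sentence without the per-cohort qualifier. Section 8.1 adds that numbers in all cohorts might be lowered considerably depending on events, and gives no rule for this.

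**The concern.** A cohort is defined by the device a patient received, or by having none, and the plan leaves that choice to the treating physician. The study therefore does not control the mix. Because 556 equals the sum of the minima, each subject enrolled above one cohort's minimum at that count is matched by a subject missing from another's. Someone who follows Section 10.4 to the letter can close enrolment with a mortality cohort well under 172.

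That could not be repaired afterwards. If a short cohort then failed its 80% survival goal, the failure could not be told apart from inadequate size, and the plan would still say the endpoint had been powered.

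**Working it through.** **Inputs.** All come from the Synopsis (Sample Size Parameters) and Table 12.1-1.
- ICD: "assuming a 95.0% ventricular arrhythmia associated symptoms free-rate, a performance goal of 85.0%, one-sided alpha level of 0.025, 90% power, and 20% attrition"; 93 analysed, 117 enrolled.
- CRT-D: "assuming a 97.0% ventricular arrhythmia associated symptoms free-rate, a performance goal of 87.0%, one-sided alpha level of 0.025, 90% power, and 20% attrition"; 76 analysed, 95 enrolled.
- PM/CRT-P: "assuming a 90.0% all-cause mortality free-rate (survival rate), a performance goal of 80.0%, one-sided alpha level of 0.025, 90% power, and 20% attrition"; 137 analysed, 172 enrolled.
- Non-device: "assuming a 90.0% all-cause mortality free-rate, a performance goal of 80.0%, one-sided alpha level of 0.025, 90% power, and 20% attrition"; 137 analysed, 172 enrolled.
- Method: "Sample sizes for primary endpoints were calculated employing exact binomial methods in nQuery + nTerim 3.0".

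**Formula.** For n analysed subjects, let r be the smallest count with P(X ≥ r | n, p0) ≤ 0.025, where p0 is the performance goal. Power is P(X ≥ r | n, p1), where p1 is the expected rate. Enrolled number = n / (1 − attrition), rounded up.

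**Step 1: reproduce the plan.**

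| Cohort | n | r | Actual alpha | Power | n / 0.8 | Enrolled |
|---|---|---|---|---|---|---|
| ICD | 93 | 86 | 0.0235 | 90.6% | 116.25 | 117 |
| CRT-D | 76 | 72 | 0.0241 | 92.2% | 95 | 95 |
| PM/CRT-P, Non-device (each) | 137 | 119 | 0.0245 | 91.0% | 171.25 | 172 |

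Each n is the smallest that reaches 90%. The table is correct, and 117 + 95 + 172 + 172 = 556.

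**Step 2: slack in 556.**
- At 20% attrition there is none against the Table 12.1-1 minima.
- At 10% the need is 93/0.9, 76/0.9, 137/0.9 and 137/0.9, rounded up: 104 + 85 + 153 + 153 = 495. That leaves 61 spare.
- With no attrition the need is 93 + 76 + 137 + 137 = 443. That leaves 113 spare.

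**Step 3: power under other splits of 556.** The documents give no expected mix, so these splits are assumptions:
- A: 139 in each cohort.
- B: 147/136/109/164 (ICD/CRT-D/PM/CRT-P/Non-device), in proportion to the upper limits 270/250/200/300.
- C: 200/150/103/103.

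Analysed n is the enrolled number times (1 − attrition), rounded down. For the mortality cohorts p0 = 0.80 and p1 = 0.90.

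| Enrolled in a mortality cohort | 20% attrition | 10% attrition | None |
|---|---|---|---|
| 172 (plan) | n = 137: 91.0% | n = 154: 91.1% | n = 172: 94.0% |
| 139 (A, both) | n = 111: 78.2% | n = 125: 88.1% | n = 139: 90.0% |
| 109 (B, PM/CRT-P) | n = 87: 62.9% | n = 98: 72.7% | n = 109: 80.1% |
| 103 (C, both) | n = 82: 69.7% | n = 92: 68.7% | n = 103: 77.2% |

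Exact binomial power is saw-toothed because r is a whole number. That is why 103 enrolled shows more power than 109 at 20% attrition, and why 103 shows slightly less at 10% than at 20%.

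**The case against.** The strongest reply is that the cohort floors are already in the plan. The ranges and Table 12.1-1 state them, the Synopsis low-enrolment sentence applies them cohort by cohort, and the trigger only permits closure to begin. Read together, 556 is shorthand for four filled cohorts. This stands in part: the minima are not missing, and nothing shows that the sponsor means to close a cohort short. But Section 10.4, the operative section, refers to none of these floors, and Sections 8.1 and 12.1.6 contain looser wording.

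A reader might infer that 556 gives 90% power only if the split is exactly 117/95/172/172. The documents do not support that. Section 12.1.6 treats 20% attrition as an upper limit, and at lower attrition other splits suffice (step 2). Even at 20%, rounding leaves a spare subject in three cohorts: 116 ICD enrolled less 23 leaves 93, and 171 less 34 leaves 137.

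A reader might also infer an equal threat to all four primary tests. The Synopsis makes the combined ICD and CRT-D analysis primary and the separate ones descriptive, and it gives no combined goal or power. Section 12.1 still sets a goal for each. The argument is therefore clear only for PM/CRT-P and Non-device.

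Finally, Section 12.1 analyses by Kaplan-Meier with log-log bounds and censors lost subjects at last contact. They still contribute follow-up, so dropping them from a binomial test probably overstates the loss. This weakens the exact figures but not the direction.

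**Conclusion.** The concern holds as an unreconciled conflict between a pooled closing rule and per-cohort minima. The trigger as written does not deliver the per-cohort power that the Synopsis and Section 12.2.2 attach to 556. Under the assumed splits, a mortality cohort designed for about 91% power falls to roughly 63–78% at the planned 20% attrition, and to roughly 77–90% with none. At no attrition the equal split costs almost nothing, while the less balanced splits still fall well short.

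These sizes rest on the plan's own rates and alpha, on splits the documents do not predict, and on a binomial approximation to the planned analysis. That the pooled count fails to protect a cohort minimum does not depend on those assumptions.

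**What to change.** - **Synopsis, 8.1 and 10.4:** let closure begin only when every cohort has reached its own Table 12.1-1 minimum (117, 95, 172, 172).
- **12.1.6:** add the per-cohort qualifier to the low-enrolment sentence so that it matches the Synopsis.
- **8.1:** reconcile the statement that numbers may be lowered depending on events with this condition.
- **Synopsis and 12.2.2:** say that 556 gives about 90% power per cohort only when each cohort minimum is met. Section 12.2.2 contains no closure trigger, so only its power claim changes. The word about is needed because exact power dips between steps: 120 ICD enrolled gives 96 analysed and 89.2%.
- **If the pooled trigger is kept:** withdraw the claim that 556 powers each cohort.

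The edits are a few sentences. The cost is that the slowest cohort may stay open longer and the total may pass 556. The stated ceilings (950 in the Synopsis, 8.1 and 10.4; 900 in 12.2.2) leave room, provided full cohorts can be closed individually. If ICD, CRT-D and Non-device all ran to their upper limits (270 + 250 + 300 = 820), only 130 places would remain under 950 for PM/CRT-P.
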